7.3.5.4 Post partum follow up of mothers with flare

The majority (95%) of the women will have the study endpoint at 6 months. However, if flare is detected, these women will be followed for a further 6-9 months and provided with drug therapy where monitoring shows it is required.

7.3.5.5 Post-partum follow up of infants

The following will be performed:

- Evaluation of growth at 1, 2, 4 and 6 months
- Vaccinations at 2, 4, and 6 months
- TDF drug concentration at 1 month
- Test for HBsAg at 2 months with a 3 mL venepuncture sample.

7.3.6 Subjects transferred to another hospital

If a subject needs to be referred to another hospital for an adverse event, such woman is still considered to be in the study and attempts will be made to obtain relevant data and follow them up after hospital discharge in accordance with the study schedule.

8. Notes on study procedures / investigations

8.1 Clinical

On the days of the dense PK sampling, vital signs will be done just before the blood sample to obtain an accurate blood pressure measurement in the absence of pain/stress associated with taking the blood sample.

A more detailed physical examination will be conducted if clinically indicated by the reported symptoms and the vital sign data. Further investigations will be done as clinically indicated. See on Adverse Events.

8.2 Blood sample collections

The total blood volume of blood over the course of the study for the mother depends on the timing of enrollment and the details are provided in the sample collection table below. On average a woman who commences participation in trimester 2 will give 144 mL total while participation commencing in trimester 3 will provide 96 mL total.

8.2.1. Mother blood sample collections

A 6 ml venipuncture sample of whole blood will be collected at baseline and during monthly follow up (Table 1). Three mL will be placed in EDTA, plasma separated, and stored in 2 separate Eppendorf tubes for later testing of HBV DNA concentration. Another 3 ml will be placed in a plain tube, serum separated and (HBsAg, HBeAg at baseline) ALT, creatinine, and serum phosphate will be measured. HBV DNA and TDF concentrations will be determined. Any leftover serum will be stored frozen at -80°C.

8.2.2. Cord blood sample collections

Cord blood samples of 12 mL will be collected after the birth of the baby and before delivery of the placenta. The cord will be cleaned with a swab and a 23 g needle inserted into the umbilical cord to aspirate 12 mL with 6 mL into EDTA and 6 mL into a plain tube. The tubes will be centrifuged and resulting plasma will be aliquoted in two separate Eppendorf tubes and tested for HBV DNA and TDF concentrations. Plain tubes will be centrifuged after clot formation and serum aliquoted, and eppendorf tubes sent for HBsAg and HBeAg testing at Mae Sot, or if leftover sample, frozen at -80°C.

8.2.3. Infant blood sample collections

Infant blood sample of 3 mL at the 1 and 2 month visit will be drawn up and 1.5 mL placed into EDTA and 1.5 mL into a plain tube. Resulting plasma from the 1 month EDTA blood sample will be aliquoted in two separate Eppendorf tubes and tested for HBV DNA and TDF concentrations. Plain tubes will be centrifuged after clot formation and serum aliquoted, and Eppendorf tubes sent for HBsAg testing at Mae Sot, or if leftover sample, frozen at -80°C.

8.2.4 Breastmilk sample collection

At each sample time, staff and the participant will assess if she has adequate breast milk to collect a sample without adverse effect to the baby (eg. insufficient nutrition) or herself (eg. excessive squeezing). Participants will have the option to obtain breast milk by manual expression or using a (electronic) pump. If the woman has a cracked or bleeding nipples, this will be noted and appropriate care will be provided for the woman. If possible, milk for measurement of viral load will be collected from an intact nipple.

A. Colostrum (Viral load):

When the woman begins to have adequate colostrum production postpartum (day 1-2 on average), she will be asked to express 3 ml of colostrum into a sterile container. The woman may express from either or both breasts. Use of a breast pump will be allowed but hand expression is expected to be most effective.

B. 1 month breast milk (PK and viral load):

At hour 4 post-dose the mother will be asked to express the entire contents of one breast (choose the more full breast) into one clean container. The breast milk will be measured, mixed and a minimum of 10 ml aliquot taken. Remaining milk will be given to the mother to feed back to her infant with spoon, cup, or syringe, according to her preference. Infant feeding will be allowed to continue on demand (as is the cultural norm and recommended by the WHO) between the drug dose and the breast milk sample, and exposure to the infant will be considered essentially continuous.

C. 2-6 month breast milk (viral load):

At a convenient time during the visit, the mother will be asked to express a minimum of 5 ml into one clean container.

Table 1. Sampling schedule

8.2.4 Blood tests

Pharmacokinetic measures: We will measure TFV (and HBV DNA) concentrations every month but dense sampling will occur at three periods: in second trimester between 22–26 weeks gestation (if enrolled), in third trimester between 30–38 weeks gestation and 4 weeks post-partum. During dense PK sampling, blood will be drawn via an intravenous catheter inserted before the first sample. The exact time frames are shown in Table 2, where 0 is the sample before the first dose of TDF.

Table 2. PK sampling times

PK: Whole blood into EDTA tubes will be taken and spun down at 1500-2000 ×g for 10 minutes to obtain plasma. The plasma will then be aliquoted in two separate cryovials, labelled and stored at minus 80°C until analysis in the laboratory of [name] in Nijmegen, the Netherlands. This laboratory is accredited (NEN-EN-ISO 15189) and uses an in house validated Liquid chromatography–mass or tandem-mass spectrometry (LC-MS/MS).

Biochemistry: creatinine, ALT and phosphorus and HBV DNA (1st and delivery cycle): Another aliquot of whole blood 6 mL of blood will be drawn up and 3 ml put into EDTA and 3 ml into a plain tube. EDTA will be processed immediately. Blood will be centrifuged to separate plasma and serum for 5 minutes.

Plasma will be used for HBV DNA quantification using the HBV DNA assay Fast Track Diagnostics (<http://www.fast-trackdiagnostics.com/human-line/products/ftd-hepatitis-b-dna/>). Remaining serum or plasma will be stored at -80°C in case any test result need clarification.

8.3 Sample labelling

Study samples, including stored samples, will be labelled with:

- Subject number
- Date of specimen collection
- Time specimen collection
- Type of specimen

8.5 Safety net

The net will include:

- Pre-study training will be given to the study team with an emphasis on:
 - taking informed consent
 - performing monthly clinical assessments
 - making it easy to ask for a consult by senior colleagues
 - explaining how to use the TDF stopping rule as a guide (eg. kidney failure or ALT rise due to TDF treatment, see 13.3.1)
- check for hepatic flare (see 13.3.1)

9. Drug Management

9.1 Supply Storage and Handling

All TDF tablets in this study should be kept in a controlled room temperature (25°C or 77°F); excursions permitted between 15°C to 30°C (59°F to 86°F).

9.2 Drug Accountability

SMRU clinics will maintain a record of the numbers of all TDF tablets obtained, used by the subjects and returned to the pharmacy. These information will be recorded in the drug accountability record during the study. On study completion, a copy of the drug accountability record will be filed in the study folder. Unused TDF will be returned to the SMRU pharmacy.

9.3 Concomitant Medications

Subjects may develop minor illnesses during follow up. These will be treated by the research team.

Drugs that may cause kidney failure or interfere with the metabolism of TDF must be prohibited throughout the study participation. (e.g. aminoglycosides (e.g., gentamicin), and high-dose or multiple NSAIDs.

10. Discontinuation/Withdrawal of Participants from Study

Each subject has the right to withdraw from the study at any time. In addition, the Investigator may discontinue a subject from the study at any time if the Investigator considers it necessary for any reason.

10.1 Voluntary withdrawal of consent

Subjects may withdraw from the study at any time and for any reason.

10.2 PI withdrawal

A subject will be withdrawn by the PI from the study if:

- Significant protocol deviation (for example not taking medication for >2 months)
- Subjects experience adverse drug reaction that may affect their safety during the study as judged by the investigator
- Significant non-compliance with treatment regimen or study requirements
- Loss to follow up (>3 visits)

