7.3.5.3 Post-partum follow up of mothers

The subject will be followed up monthly until 6 month post-partum. The following procedure will be performed on the mothers:

- Physical examination and vital signs at each post-partum visit.
- TDF will be continued until one month post-partum to theoretically decrease the risk of flares as their immune system returns to baseline.
- The last dense PK sampling will occur at 4 weeks post-partum.
- At the 1 month post-partum follow up, the woman will again have dense PK sampling of her blood. A single breastmilk sample will be taken 4 hours after drug dosing.
- At the 1 month post-partum visit, Creatinine will be measured, if Creatinine is increased (\geq 1.5 times from the baseline) this will be repeated according to routine care.
- The last blood sampling on PK (single blood sample) will be at the 2 month post-partum.
- At the 1 and 4 months post-partum visits, ALT will be measured (from 5ml and 2 ml respectively). If ALT is increased with a Grade 3 or higher (described in 13.3.1) but there is not a true flare, the ALT will be repeated at 6 months post partum.

- At each post-partum visit month 1 to month 6, breastmilk samples will be collected and blood samples will be collected for HBV DNA tests

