10.3 Management of withdrawn subjects

The care of pregnant women that have been withdrawn from the study will continue through the delivery and post-partum period irrelevant of the reason for withdrawal. It is important for pregnant women to receive proper antenatal, delivery and post-partum care. The data collected until the point of withdrawal will be included in the study and this is stated in the participant information sheet. The reason for withdrawal will be recorded in the CRF. If a subject withdraws after receiving TDF, Alanine transaminase (ALT) testing will be done (when possible) to monitor for hepatic flare. Every effort will be made to make sure that the subject understands this. Participants who withdraw will be replaced as complete sample sets are necessary for the analysis.

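### PI withdrawal under 10.2 ends the whole study for a woman, so the 12.2.2 infant-infection proportion would probably omit pairs with stopped or interrupted TDF; a wording change would keep them

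*Combined protocol and SAP*

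**What the plan says.** Section 10.2 opens "A subject will be withdrawn by the PI from the study if" and lists four reasons: significant protocol deviation (the example is more than two months without medication), a safety-relevant drug reaction ("Subjects experience adverse drug reaction that may affect their safety during the study as judged by the investigator"), significant non-compliance with treatment or study requirements, and loss to follow-up. It gives no intermediate option of stopping drug or dense sampling while staying in follow-up.

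Section 10.3 sets out what happens next. Clinical care goes on through delivery and post-partum. On data, "The data collected until the point of withdrawal will be included in the study". On tests, "If a subject withdraws after receiving TDF, Alanine transaminase (ALT) testing will be done (when possible) to monitor for hepatic flare". On numbers, "Participants who withdraw will be replaced as complete sample sets are necessary for the analysis".

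The samples at issue are scheduled elsewhere. Section 7.3.5.2 and Appendix C take cord blood for HBsAg, HBeAg, HBV DNA and drug concentration. Section 7.3.5.5 lists "Test for HBsAg at 2 months with a 3 mL venepuncture sample". Section 8.2.3 has plasma from the "1 month EDTA blood sample will be aliquoted in two separate Eppendorf tubes and tested for HBV DNA and TDF concentrations". For mothers, 7.3.5.3 says that at each visit from month 1 to month 6 "breastmilk samples will be collected and blood samples will be collected for HBV DNA tests".

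Section 12.2.2 lists, as a secondary endpoint, the proportion of infants positive for HBsAg and HBV DNA in cord blood and for HBsAg at 2 months. It states no denominator, and 12.3 has no rule for infants of withdrawn women.

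**The concern.** Withdrawal from the study suits a steady-state PK aim: a woman off drug cannot supply an interpretable dense curve, and replacing her is sensible. The infant endpoint is a different matter. The women removed are those whose TDF was stopped or interrupted, and section 13.4.1 gives fewer infected children as the potential benefit of TDF. A link between the withdrawal reasons and infant risk is therefore plausible, but it is an inference; the documents give no risk by adherence. If withdrawn pairs are not tested and are replaced by women who complete, the reported proportion no longer covers everyone treated. Cord blood and a 2-month sample that were never taken cannot be recovered later, and with about 24 infants each result carries about 4 percentage points (1/24 = 4.2%).

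**Working it through.** **The plan's own figure.** Section 12.1 states 60 dense PK curves. Twelve second-trimester enrolees × 3 periods + twelve third-trimester enrolees × 2 periods = 36 + 24 = 60. It reproduces. It also shows that the replacement rule serves the PK sample sets. No withdrawal rate is given anywhere, so the number withdrawn is an assumption below.

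**Do other sections keep the samples?**
- 7.3.6 keeps a woman in the study when she is referred to another hospital for an adverse event. It covers transfer, not withdrawal under 10.2.
- 8.5 refers to a TDF stopping rule (kidney failure, ALT rise), so stopping drug is foreseen. It does not say what sampling follows.
- 11.5 follows an adverse event until it resolves or stabilises.
- 13.2 adds three months of flare monitoring, for the mother.
- 13.3.1 says all women stay on study to the 4-month post-partum visit, but within the hepatic-flare text, where ALT is the only test named.

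None clearly continues cord, infant or HBV DNA sampling after withdrawal.

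**What is lost, by time of withdrawal** (Appendix C; HBV DNA points at delivery and months 1–6, in blood and milk):
- Before delivery: cord result, 2-month infant HBsAg, and 7 blood + 7 milk points, plus any monthly pregnancy HBV DNA samples still due.
- After delivery, before the 1-month visit: 2-month HBsAg and 6 + 6 points. The cord result is kept under 10.3.
- After the 1-month visit, before the 2-month visit: 2-month HBsAg and 5 + 5 points.
- If 13.3.1 is read as covering withdrawn women: only months 5 and 6, that is 2 + 2 points. That reading contradicts 10.2.

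**Effect on the infant proportion.** Let 24 retained pairs have results and k withdrawn pairs have none. With p_R and p_W the proportions positive among retained and withdrawn pairs, the all-treated proportion is (24·p_R + k·p_W)/(24 + k). The retained figure differs from it by [k/(24 + k)] × (p_R − p_W), which is zero when the two are equal.

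Take 0 positive among 24 retained as the scenario. The Clopper-Pearson 95% interval for 0/24 is 0 to 1 − 0.025^(1/24) = 14.2%. The all-treated proportion then lies between 0 and k/(24 + k), whatever the risk in withdrawn pairs:
- k = 1: 1/25 = 4.0%
- k = 2: 2/26 = 7.7%
- k = 3: 3/27 = 11.1%
- k = 4: 4/28 = 14.3%, about the upper limit of the interval

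For an expected value, assume a risk r of 0 to 32% in withdrawn pairs. Zero is allowed because HBeAg-negative women are eligible and section 2 gives 0–30% for them; 32% is the top of the prevention-failure range in section 2, borrowed only as a scale. Then k·r/(24 + k) is at most 0.32/25 = 1.3%, 0.64/26 = 2.5% and 0.96/27 = 3.6% for k = 1, 2 and 3, and 0 at the lower end.

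**The case against.** The strongest reply is that the loss is never stated. Section 8.5 has a stopping rule separate from withdrawal, 10.2 applies to a drug reaction only where the investigator judges safety may be affected, and 13.3.1 says all women stay on study to 4 months, which would preserve both the cord and the 2-month infant results. This stands in part: the loss is the natural reading of 10.2 and 10.3, not an express one. But 8.5 says nothing about follow-up and 13.3.1 is flare text, so the plan leaves the matter open at best.

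The second reply is that few women will be affected. The adherence triggers say significant, and milder non-adherence stays in. Under 6.2, third-trimester women enter at 28 to under 34 weeks; assuming delivery near 40 weeks, they have about 6 to 12 weeks on drug before birth, so many could not be off drug for more than two months by then. Counselling, pill counts and DOT also help. This stands, although the non-compliance reason has no time limit. A reader might infer that the infant proportion would describe mainly adherent, tolerant women. The documents do not support that: the filter acts only on significant cases, probably few.

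Third, the 1-month infant draw adds little once the mother has stopped TDF, and its HBV DNA result is not part of the 12.2.2 endpoint. This stands, and the fix leaves it out.

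Finally, Appendix B, the contents of Table 1 and the information sheet are not in the readable text, so the absence is confirmed only for what can be read.

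**Conclusion.** The point holds as a cheap improvement, not a major flaw. Section 10.2 makes withdrawal study-wide for three reasons tied to drug exposure, 10.3 names only ALT testing afterwards and replaces the woman, and nothing readable clearly keeps the infant results. The infant proportion would then exclude pairs with interrupted or stopped TDF.

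The size is unknown because no withdrawal rate is given. With 0/24 retained infants positive and one to three untested pairs, the all-treated proportion could be at most 4.0% to 11.1%, inside the 0–14.2% sampling interval. In that scenario the omission can only understate; in general the direction is unknown, and the bias is zero if withdrawn and retained pairs have equal risk.

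Two stronger inferences should be resisted. The primary PK aim is not harmed, since excluding women off drug from dense PK sampling is reasonable. Nor is the planned post-cessation HBV DNA result shown to be biased: its question is stopping at about one month post-partum (28 days in 7.3.3), and what is lost is mainly extra information on earlier stopping. The infant proportion is itself a secondary endpoint and not among the objectives in section 4. Confidence is medium, given the ambiguity of 8.5 and 13.3.1.

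**What to change.** - **10.2:** for the deviation, adverse-reaction and non-compliance reasons, state that TDF and/or dense PK sampling is discontinued and that mother and infant remain in follow-up unless consent is withdrawn. Replace her for PK only.
- **10.3:** continue the scheduled cord HBsAg and HBV DNA, the 2-month infant HBsAg and maternal ALT. Continue maternal blood and milk HBV DNA as scheduled, and report it separately as early cessation. Omit the 1-month infant TFV draw if the mother has stopped TDF.
- **12.2.2:** report the infant proportion over all women who received TDF, with the number missing.

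This wording settles the matter whichever way 13.3.1 is read. The cost is protocol, CRF and information-sheet wording, plus a few already-scheduled samples per retained pair: at most one cord set, one 3 mL infant draw, 7 blood and 7 milk HBV DNA assays from delivery on, any monthly pregnancy samples still due, and ALT. These women already stay in care under 10.3. The change will not recover women lost to follow-up or unwilling to give samples, and voluntary withdrawal is untouched.

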10.3 Management of withdrawn subjects

The care of pregnant women that have been withdrawn from the study will continue through the delivery and post-partum period irrelevant of the reason for withdrawal. It is important for pregnant women to receive proper antenatal, delivery and post-partum care. The data collected until the point of withdrawal will be included in the study and this is stated in the participant information sheet. The reason for withdrawal will be recorded in the CRF. If a subject withdraws after receiving TDF, Alanine transaminase (ALT) testing will be done (when possible) to monitor for hepatic flare. Every effort will be made to make sure that the subject understands this. Participants who withdraw will be replaced as complete sample sets are necessary for the analysis.

10.4 Study Discontinuation

The study may be discontinued by the ethics committee/s and/or the study sponsor. Reasons for terminating the study may include, but are not limited to, the following:

- The incidence or severity of AEs indicating a potential health hazard to participants
- Investigators do not adhere to the protocol

11. Subject Safety monitoring & adverse event reporting

This study will use the Common Toxicity Criteria v 5.0 for grading adverse events. It is available from this website:

https://ctep.cancer.gov/protocoldevelopment/electronic_applications/docs/ctcae_v5_quick_reference_5x7.pdf

11.1 Adverse Events

From the time TDF is started through the end of the study, the subjects will return for monthly study visits (timed with routine ANC visits) where a case report form, an adverse events (AE) form, and an adherence form will be completed. Pre-specified AEs include headache, nausea, vomiting, and ALT flares after discontinuation of TDF will not be recorded as an AE. Any unexpected AEs will be documented according to standard definitions and procedures.

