The follow-up for women will be until 6 months post-partum, to check for flares. TFV concentrations will be collected by venous blood testing but an indwelling catheter can be used during the rich sampling 24 hour period. Infants will be followed up from delivery, and at 1, 2, 4 and 6 months of age for vaccination and growth. Infant drug exposure is measured at month 1 and HBV DNA will be measured at birth from cord blood and HBsAg by venepuncture at 2 months of age. The flow chart is available in Appendix B.

Study duration

We will enroll volunteers into this study after ethical approval. Because we will enroll subjects in gestational windows we expect the recruitment and follow up to last at least 2 years.

6 Participant identification and recruitment

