11.4 Serious Adverse Event Recording

All adverse events are recorded in the CRF. A serious adverse event (SAE) occurring to a subject should be reported to the EC that gave a favorable opinion of the study where in the opinion of the Chief Investigator the event was ‘related’ (resulted from administration of any of the research procedures) and ‘unexpected’ in relation to those procedures. Reports of related and unexpected SAEs should be submitted within 5 working days of the Chief Investigator becoming aware of the event, using the SAE form.

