12.2 Study endpoints

12.2.1 Primary endpoint

The primary endpoint is the Dense TDF concentration for 24 participants repeated at 3 gestational periods (2nd and 3rd trimester of pregnancy and 1 month post-partum). The end of the study is the date of the last visit to the clinic by a study subject which is anticipated as when the last infant involved in the study reaches 6 months of age.

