12.3 Data Analysis

Data cleaning will be performed prior to analysis to identify incomplete and incorrect data. All women will be censored at delivery for the analysis. Detailed statistical methods are described below.

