12.3.1 Continuous data

These data will be summarized by medians (ranges) and means (standard deviations), as appropriate, and will include the biochemical parameters.

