13.3 Risks

13.3.1 Risks of oral TDF

TDF is globally being used in pregnant women for prevention of mother to child transmission of HIV. It is generally well tolerated with the most common adverse reactions identified from any of the large controlled clinical trials include rash, diarrhea, headache, pain, depression, asthenia, and nausea.(16, 17)

Other side effects are:

- Kidney failure defined as:

- A rise in serum creatinine \geq 1.5 times from the baseline OR
 - An absolute rise in serum creatinine of \geq 26.5 $\mu\text{ml/L}$ (\geq 0.3 mg/dl) within 48 hours

- ALT rise to Grade 3.

Grade 3 or higher is >5 x upper limit of normal (ULN) if baseline levels were below the ULN; or if baseline levels were $>$ ULN and, then grade 3 or higher is >3.5 x baseline value. The normal value of ALT will be defined as 0-31 U/L.(18)

- Hepatic flare

A tangible adverse consequence that requires further study is the potential for hepatitis flare following discontinuation of therapy in the mother. All women will continue on study until the 4 month post-partum visit. At the 1 and 4 months post-partum visits ALT will be measured (from a 5ml and 2 ml blood sample respectively). If 3 months after stopping TDF, a flare is detected (ALT >5 x baseline if this was increased at baseline or >10 x the upper limit of normal with no alternative diagnosis) the woman will continue to be monitored until resolution of the flare. If the flare worsens or does not resolve they will be placed on anti-HBV therapy and be reviewed by a physician. If ALT is increased but there is not a true flare,

(ALT>3.5x baseline if this was increased at baseline or >5x the upper limit of normal), they will be followed for an additional 6-9 months and repeat ALT testing done at 6 months.

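### As worded, 11.1 keeps ALT flares after TDF is stopped out of adverse event recording, at odds with 11.4 and 13.3.1, and section 12 plans no flare count

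*Combined protocol and SAP*

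**What the plan says.** **Recording.** The sentence in 11.1 opens by naming headache, nausea and vomiting as pre-specified adverse events and then runs on: "ALT flares after discontinuation of TDF will not be recorded as an AE". Section 11.4 states: "All adverse events are recorded in the CRF". It gives no exception.

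**Status of flare.** Section 13.3.1 puts hepatic flare in its list of other side effects and writes: "A tangible adverse consequence that requires further study is the potential for hepatitis flare following discontinuation of therapy in the mother". It defines a flare by ALT, relative to the woman's own baseline if that was raised or to the upper limit of normal (ULN), provided no other diagnosis explains the rise. Section 5 says: "The follow-up for women will be until 6 months post-partum, to check for flares". Appendix C schedules adverse event assessment at every post-partum visit to month 6.

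**Analysis.** Section 12.2 lists drug concentration, infant exposure, HBV DNA and infant infection endpoints, and flare is not among them. The only planned analysis that reaches ALT is in 12.3.1: "These data will be summarized by medians (ranges) and means (standard deviations), as appropriate, and will include the biochemical parameters". Section 12.3 adds: "All women will be censored at delivery for the analysis". The primary endpoint in 12.2.1 is nevertheless "repeated at 3 gestational periods (2nd and 3rd trimester of pregnancy and 1 month post-partum").

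**Monitoring.** ALT is measured at 1 and 4 months post-partum, and at 6 months if raised (7.3.5.3, 13.3.1). Women who flare are followed for longer (7.3.5.4), and women who withdraw after taking TDF have ALT tested where possible (10.3).

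**The concern.** TDF is given until 28 days post-partum, so most of the post-partum follow-up is off treatment. The protocol collects adverse events throughout that time, yet as worded it leaves out the one off-treatment event that it singles out as needing study. Staff completing the adverse event form would follow 11.1 and enter nothing.

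Three things follow. The adverse event data would be silent on post-treatment flares. Section 10.4 names the incidence or severity of adverse events as a possible reason to end the study, and unrecorded flares would not enter that incidence. And because section 12 plans no flare count, no planned output would say how many women flared after stopping TDF, although ALT is measured for that purpose.

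Section 11.1 is also silent on a flare that meets a seriousness criterion in 11.6.

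**Working it through.** **1. How 11.1 can be read.**

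| Reading | Are post-TDF flares recorded as adverse events? |
|---|---|
| Headache, nausea and vomiting are pre-specified; flares are excluded | No |
| All four listed items are excluded | No |
| Drafting error: flare was meant as a fourth pre-specified event | Yes, but only by setting aside the closing words |

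Both readings that keep the words as written exclude flares. The third means that the sentence needs correcting.

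**2. Against the other sections.** Section 11.4 allows no exception, and 13.3.1 classes flare as a side effect. If flares are deliberately defined as not being adverse events, neither 11.1 nor 11.4 says so. Sections 11.6 and 11.7 do not exempt a flare that is serious, and 11.1 does not refer to them.

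**3. Does 12.3.1 fill the gap?** Inputs from 13.3.1: ULN 31 U/L; flare above 10 × ULN, or above 5 × baseline if baseline was raised.

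- Normal baseline: 10 × 31 = 310 U/L.
- Raised baseline of 32 U/L: 5 × 32 = 160 U/L. Raised baseline of 62 U/L: 5 × 62 = 310 U/L.

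A maximum ALT between 160 and 310 U/L may or may not be a flare, depending on that woman's baseline. A maximum also cannot say whether one woman flared or several. Medians, means and ranges therefore do not give the count.

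**4. The censoring sentence.** The plan's 60 dense curves in 12.1 are reproduced as 12 women × 3 periods + 12 women × 2 periods = 36 + 24 = 60. Each of the 24 women contributes one post-partum curve, so literal censoring at delivery would discard 24 of the 60 curves, as well as every ALT taken after TDF stops. It cannot be squared with 12.2.1, nor with the secondary endpoint in 12.2.2 on HBV DNA after cessation.

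**5. Scale.** The documents give no flare rate, so r is assumed. With n = 24, P(at least one) = 1 − (1 − r)^24.

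| Assumed r | Expected flares, 24r | P(at least one) |
|---|---|---|
| 1% | 0.24 | 1 − 0.99^24 = 0.21 |
| 5% | 1.2 | 1 − 0.95^24 = 0.71 |
| 10% | 2.4 | 1 − 0.90^24 = 0.92 |

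Detected flares may be fewer. After TDF stops, 7.3.5.3 and 13.3.1 schedule ALT for all women at month 4 only, with month 6 conditional. Section 7.3.4 says monthly, but in the context of evaluating the TDF regimen.

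**6. Precision of a count.** Exact (Clopper-Pearson) 95% intervals: 0/24 gives 0 to 14.2%; 1/24 gives 0.1% to 21.1%; 2/24 gives 1.0% to 27.0%.

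**The case against.** The best defence is that 11.1 is a specific carve-out: post-cessation flares are defined as not being adverse events, so 11.4 is not literally contradicted. Flares have their own pathway of ALT tests, thresholds and extended follow-up, and anyone could derive the count later from the stored ALT. This is a descriptive PK study of 24 women with no flare objective.

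Much of this stands. A carve-out is a possible intention, no ALT data are lost, and flare is not a stated objective. But a carve-out would have to be stated, with a rule for serious cases. A count that can be derived is not a planned output.

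Four stronger inferences should be resisted:

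- *Flares go unmonitored or untreated.* Sections 7.3.5.3, 7.3.5.4, 10.3 and 13.3.1 show otherwise.
- *Moderate ALT rises are recorded while the largest are not.* This assumes that 11.1 uses the 13.3.1 flare threshold. Section 11.1 gives no definition, 13.3.1 distinguishes a true flare from lesser rises, and Appendix C refers to suspected as well as confirmed flares.
- *The protocol expects 5% of women to flare.* Section 7.3.5.4 says only: "The majority (95%) of the women will have the study endpoint at 6 months". Section 13.3.1 also extends follow-up for women with raised ALT but no true flare, so the remaining 5% need not all be flares.
- *Only flares lack a summary.* Section 12 plans no adverse event summary at all, so correcting 11.1 alone would add nothing to the planned outputs.

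**Conclusion.** The concern holds as a gap in safety recording and reporting. As worded, 11.1 is inconsistent with 11.4, 13.3.1 and section 5, and nothing in section 12 would report how many women flared. The censoring sentence makes this worse if taken literally.

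The conclusion rests on the text and needs no assumed flare rate. The rate bears only on how likely the gap is to matter in practice: for an assumed 1% to 10%, the chance of at least one flare in 24 women is 21% to 92%. Confidence is moderate, because the sentence in 11.1 is garbled and its intent cannot be known from the documents. The sponsor should correct it. The point does not touch the primary PK objective, except through the censoring sentence.

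**What to change.** 1. **Sections 11.1, 11.4 and 13.3.1.** Reconcile them, giving flares a sentence of their own in 11.1, for example: *Post-treatment ALT flares are entered in the CRF as adverse events, graded under 11.2 and assessed for relatedness under 11.3; any that meets 11.6 is reported under 11.7.* Splitting the sentence also settles whether headache, nausea and vomiting are recorded. Whether a flare counts as expected or unexpected is for the sponsor to decide.

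2. **Section 12.3.** Add a descriptive n/N with an exact 95% interval for women who meet the 13.3.1 flare definition after TDF stops, including its condition that no other diagnosis explains the rise. N is the number of women with at least one ALT after TDF stops. Report separately the number above the ALT threshold whatever the diagnosis, and the number with no ALT after TDF stops. State the time window, since 13.3.1 refers to detection 3 months after stopping.

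3. **Censoring sentence in 12.3.** Reconcile it with the post-partum endpoints in 12.2.1 and 12.2.2 for the whole analysis, because as written it would also exclude the flare count.

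The cost is a few sentences and a few CRF entries. The interval will be wide, so the result is descriptive only. No additional ALT test is needed, and clinical management does not change.
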